### **5.4.3 Data handling conventions for immunogenicity variables**

#### ***Computed values for analysis***

In order to appropriately manage replicate values for analysis purpose, the individual GMT of all values will be computed for each blood sample after managing extreme values as described. The computed value is then considered the titer for that particular blood sample.

- If a titer is <lower limit of quantification (LLOQ), then the computed value, LLOQ/2, will be used
- If a titer is  $\geq$ LLOQ and <upper limit of quantification (ULOQ) (or  $\leq$ ULOQ), then the titer itself will be used
- If a titer is  $\geq$ ULOP (or  $>$ ULOQ), then computed value, ULOQ, will be used.

No test or search for outliers will be performed.

### ***Fold-rise***

The derived endpoint fold-rise is driven by both baseline and post-vaccination computed values which are computed as described above. The computed value for fold-rise is:

Computed value = Post-vaccination computed value / Baseline computed value.

For HAI assay, if the computed value is  $\geq 4$ -fold rise, then the derived 4-fold rise indicator will be “Yes” for that test, otherwise the corresponding indicators will be “No.” If baseline or post-vaccination value is missing, the fold-rise is missing.

### ***Seroconversion***

Seroconversion is defined for HAI assay as either

- A computed value of HAI titer  $< 10$  [1/dil] at D0 and post-injection titer  $\geq 40$  [1/dil] at D28
- A computed value of HAI titer  $\geq 10$  [1/dil] at D0 and a  $\geq 4$ -fold increase in HAI titer [1/dil] at D28

## **5.4.4 Missing data**

For categorical variables, patients with missing data are not included in calculations of percentages unless otherwise specified. When relevant, the number of patients with missing data is presented.

### ***5.4.4.1 Safety***

Generally, no replacement of missing data will be done. Nevertheless, missing relationship will be considered as related at the time of the statistical analysis. No search for outliers will be performed. In all subject listings, partial and missing data will be clearly indicated as missing.

### ***Immediate***

For unsolicited non-serious systemic AEs, a missing response to the “Immediate” field is assumed to have occurred after the 30-minute surveillance period and will not be imputed.

For SAEs, missing or partially missing elapsed time from vaccination recorded if within 24 hours will remain missing and not be imputed. Such SAEs will not be considered as immediate.

### ***Causality***

Missing causality (relationship) for unsolicited non-serious AEs and SAEs will be considered at the time of analyses as related to vaccination.

## ***Measurements***

Partially missing temperatures will be handled as described in “Daily intensity” of [Section 5.4.2.1](#).

## ***Intensity***

For solicited reactions, missing intensities will be handled as described in “Daily intensity” of [Section 5.4.2.1](#). For unsolicited non-serious AEs, missing intensities will remain missing and will not be imputed.

## ***Start Date and Stop Date***

Missing or partial missing start dates for unsolicited AEs will remain missing and not be imputed. If either the start or stop date is missing or partially missing, the time of onset will be considered to be missing. Nevertheless unsolicited AEs with missing time of onset will be included in analyses according to the visit collected.

Missing or partially missing stop dates for AEs (solicited reactions and unsolicited AEs) will remain missing and not be imputed.

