### **Unsolicited AEs**

The summary of unsolicited AEs within 7 days after vaccine injection with the details below will be generated:

- Immediate unsolicited AE and AR (any and Grade 3)
- Unsolicited AE and AR
- Unsolicited non-serious AE and AR (any and Grade 3)
- Unsolicited non-serious injection site AR (any and Grade 3)
- Unsolicited non-serious systemic AE and AR (any and Grade 3)
- SAE
- AESI

The summary of unsolicited AEs within 28 days after vaccine injection will also be generated.

The unsolicited non-serious AEs and ARs within 28 days after vaccine injection will also be summarized by maximum intensity, time of onset, and duration.

The AE summaries after vaccine injection of [Table 6](#) will be generated with number (%) of subjects experiencing at least one event. In the summaries, the 95% CI of proportion and number of AE/ARs will also be presented.

The all and related SAEs within 28 days after vaccine injection and during the study will also be summarized by seriousness criterion and outcome.

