### ***Time of onset***

Time of onset is derived from the start date of the unsolicited non-serious AE provided in the clinical database and the date of the vaccination:

Start date of the unsolicited non-serious AE – date of vaccination.

The time of onset should be considered as missing only if one or both of the dates are missing or partially missing.

The unsolicited non-serious AEs will be analyzed “Within 28 days”, which corresponds to AEs with a time of onset between 0 and 28 days after vaccination or missing. An AE with missing time of onset will be considered to have occurred just after the vaccination indicated by the visit number, so will be included in these tables.

Note: Unsolicited non-serious AE that occurred before vaccination (negative time of onset) or with a time of onset higher than defined above ( $>28$  days) will not be included in analysis, but will be listed separately.

Time of onset will be displayed as follows:

- D0-D3
- D4-D7
- D8-D14
- $\geq$ D15
- Missing

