### ***Duration***

Duration is derived from the start and stop dates of the unsolicited non-serious AE provided in the clinical database:

Stop date of unsolicited non-serious AE – start date of unsolicited non-serious AE + 1

The duration should be considered as missing only if one or both of the start and stop dates of the unsolicited non-serious AE is missing or partially missing.

Duration will be displayed by period as following:

- 1-3 days
- 4-7 days
- 8-14 days
- $\geq 15$  days
- Missing

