#### **5.4.2.3 SAEs**

##### ***Time of onset***

Time of onset will be computed using the same methodology than for unsolicited non-serious AEs described in [Section 5.4.2.2](#).

SAEs will be analyzed throughout the study using the following periods:

- Within 28 days after vaccine injection
- During the study (i.e., all SAEs occurred during the study)

An SAE with missing time of onset will be considered to have occurred just after the vaccination indicated by the visit number, and will be included in these tables.

Note: SAEs that occurred before vaccination (negative time of onset) will not be included in analysis but will be listed separately.

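### SAP 5.4.4.1 makes an unsolicited AE's time of onset missing when only its stop date is missing, contradicting 5.4.2.2; if programmed, ongoing non-serious AEs lose their onset category

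*SAP*

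**What the plan says.** **SAP 5.4.2.2, Time of onset.** For unsolicited non-serious AEs, onset is the AE start date minus the vaccination date. Then: "The time of onset should be considered as missing only if one or both of the dates are missing or partially missing". The dates meant are the two in that formula. Events with onset after day 28 "will not be included in analysis, but will be listed separately". For missing onset: "An AE with missing time of onset will be considered to have occurred just after the vaccination indicated by the visit number".

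**SAP 5.4.2.2, Duration.** The stop date is used here, and here only: "The duration should be considered as missing only if one or both of the start and stop dates" are incomplete.

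**SAP 5.4.2.3, SAEs.** "Time of onset will be computed using the same methodology than for unsolicited non-serious AEs", with the matching convention "An SAE with missing time of onset will be considered to have occurred just after the vaccination indicated by the visit number".

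**SAP 5.4.4.1, Start Date and Stop Date.** For unsolicited AEs, "If either the start or stop date is missing or partially missing, the time of onset will be considered to be missing". The same paragraph keeps missing-onset AEs in the analyses, placing them by the visit at which they were collected, and rules out imputing stop dates.

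**SAP 5.4.5.** For safety analyses, it refers to Section 5.4.2 for time of onset.

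**Output.** SAP 4.7.2: "The unsolicited non-serious AEs and ARs within 28 days after vaccine injection will also be summarized by maximum intensity, time of onset, and duration". The onset rows are D0-D3, D4-D7, D8-D14, D15 or later, and Missing. Protocol 9.2.2.2 lists time to onset of unsolicited AEs as a secondary safety endpoint.

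**The concern.** One derived variable has two definitions of missing. The 5.4.2.2 rule is worded as exclusive, so it leaves no room for the extra stop-date condition in 5.4.4.1. The SAP does not say which section prevails.

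The data state on which the rules disagree is one the protocol expects. A footnote to Protocol 9.2.2.3.3 treats an AE without a stop date as ongoing at the end of the study. For events not judged related, the investigator supplies the stop date only when it becomes available.

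At stake is whether a known start date is discarded for ongoing AEs, and whether two programmers working from the same SAP would produce the same onset table.

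**Working it through.** The plan gives no figure to reproduce here, so the check applies each rule to the possible date states and to hypothetical records.

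**1. Formulas (SAP 5.4.2.2)**
- Onset = AE start date − vaccination date.
- Duration = stop date − start date + 1.

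The stop date enters duration only.

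**2. Date states, vaccination date known**

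| Start | Stop | Onset under 5.4.2.2 | Onset under 5.4.4.1 |
|---|---|---|---|
| known | known | known | known |
| known | missing | known | **missing** |
| missing | known | missing | missing |
| missing | missing | missing | missing |

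The rules differ in one state: start known, stop missing. A partial stop date acts in the same way.

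**3. Hypothetical non-serious AEs**

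| Start | Stop | Row under 5.4.2.2 | Row under 5.4.4.1 |
|---|---|---|---|
| D2 | D5 | D0-D3 | D0-D3 |
| D2 | none | D0-D3 | Missing |
| D6 | none | D4-D7 | Missing |
| D10 | none | D8-D14 | Missing |
| D20 | none | D15 or later | Missing |
| D31 | D33 | listed separately | listed separately |

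The four ongoing events stay in the 28-day totals under either rule, because both sections keep missing-onset AEs in the analysis. Only the onset row changes.

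**4. Events starting after D28**

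V02 falls on D28 with a window of +7 days, so at the latest on D28 + 7 = D35. The onset days that lie after D28 but by V02 number V02 − 28, that is 0 if V02 is on D28 and at most 7 (D29 to D35).

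Take a non-serious AE starting on D30 with no stop date, and V02 on D33.
- Under 5.4.2.2, onset is 30. Since 30 > 28, the event is listed separately.
- Under 5.4.4.1, onset is missing, and the result depends on the placement convention. If the event is taken as just after the vaccination (there is only one), it counts within 28 days. If it is placed by visit of collection, the SAP does not say what an event collected at V02 becomes.

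The same record as an SAE belongs only to the during-the-study period under 5.4.2.3. Under 5.4.4.1 with the first placement reading, it also enters the 28-day period.

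**5. SAEs and the 7-day overview**

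SAP 4.7.2 lists no onset-category table for SAEs, so the row shift in step 3 does not arise for them there. However, footnote a of SAP Table 6 calls for an SAE overview within 7 days. If missing onset is read as just after vaccination, an ongoing SAE could be counted there too. The missing-onset convention in 5.4.2.3 is stated for the 28-day and whole-study periods, so this remains a possibility only.

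**6. What cannot be calculated**

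Neither document gives the number or share of AEs without a stop date, or AE counts or durations by onset row.

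**The case against.** The best defence is that the SAP already shows which rule it intends. Section 5.4.2.2 has the explicit formula, 5.4.2.3 adopts it for SAEs, and 5.4.5 names Section 5.4.2 as the place where onset for safety analyses is set out. The condition in 5.4.4.1 looks like the duration rule attached to the wrong variable. Missing is also a displayed row, so any shift would be visible, and the safety analyses are descriptive with no testing planned.

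Most of this stands, and it makes the harm less likely. It does not remove the sentence. Section 5.4.4 is the SAP's dedicated missing-data section, and 5.4.2.4 itself sends the reader there for missing causality, so a programmer could reasonably follow it.

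Other limits also stand. Stop dates of related AEs are actively solicited (Protocol 9.2.2.3.3), and related AEs are followed beyond the subject's participation (Protocol 5.1.4), so they are less exposed. Subjects are told to record other events for 28 days, although Protocol 5.1.1 collects AEs to V02; few D29-D35 events may therefore be recorded.

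A reader might infer three stronger points that the documents do not support:
- **That the D15-or-later row loses most.** Onset on D15-D28 leaves 28 − 28 = 0 to 35 − 15 = 20 days before V02, against 28 − 3 = 25 to 35 − 0 = 35 for D0-D3. Time to V02 alone does not settle the matter: the loss depends on how many AEs fall in each row and how long they last, and neither is given.
- **That ongoing events after D28 must enter the 28-day tables.** This follows under one placement convention and is unclear under the other.
- **That AEs drop out of the 28-day totals.** They do not.

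**Conclusion.** The contradiction is certain on the text and needs no assumption. Its main consequence is conditional: if 5.4.4.1 rather than 5.4.2.2 is programmed, every ongoing non-serious AE within 28 days that has a recorded start date moves to the Missing onset row.

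A secondary consequence is less certain. Ongoing AEs or SAEs that start after D28 and by V02 could be counted within 28 days, and SAEs possibly in the 7-day overview, depending on how the two placement conventions are reconciled. Few such events are expected.

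The size cannot be computed, and no onset row can be singled out. The effect is confined to descriptive safety tables. D0-D28 counts in the 28-day tables, onset of solicited reactions and the primary immunogenicity conclusion are unaffected. This is a minor point, worth correcting because the rule as written is wrong and the correction is simple.

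**What to change.** In SAP 5.4.4.1, replace the sentence on missing onset with one stating that onset is missing if the AE start date or the vaccination date is missing or partial, and that a missing or partial stop date makes only the duration missing. Program onset for unsolicited AEs and SAEs as in 5.4.2.2.

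The cost is one SAP sentence and a check of the onset derivation. No new data are needed and no endpoint changes.

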## ***Action taken***

Missing actions taken will remain missing and not be imputed.

### ***5.4.4.2 Immunogenicity***

LLOQ and ULOQ management will be performed as described in “Computed values for analysis” of [Section 5.4.3](#). No test or search for outliers will be performed.

No replacement will be done for missing values. Based on the previous TIV-HD, QIV-HD, and QIV-SD studies in this population, the amount of missing immunogenicity data is expected to be  $\leq 5\%$  in this study. Usually in vaccine studies, it seems generally reasonable to assume missing immunogenicity data are missing completely at random (MCAR) (3). Indeed, it is highly unexpected that the dropout (or any other reaction for missing data) could be linked to the immune response of the subject.

### ***5.4.5 Windows for time points***

#### ***Analysis windows for time points***

A measurement at each visit will be used for immunogenicity according to following table defined in the protocol. Solicited reactions and unsolicited (non-serious/serious) AEs observed at time of onset mentioned in [Section 5.4.2](#) will be analyzed for safety analyses.

**Table 12 – Study procedure window definition**

Visit / Contact	Visit 1 (V01)	Visit 2 (V02)
Study timelines (days)	0	28
Time windows (days)	NA	[+7 days]

#### 5.4.6 Pooling of centers for statistical analyses

All data from each center will be pooled and analyzed as Enrolled subjects, Randomized subjects, FAS, PPAS, and SafAS.

#### 5.4.7 Statistical technical issues

##### *Confidence interval for the individual group GMT and GMTR*

The 2-sided 95% CI for the individual group GMT and GM of individual titer ratio (GMTR) will be computed using the normal approximation as follows:

$$10^{(\bar{x} \pm t_{n-1, \alpha/2} \sqrt{v(\bar{x})})},$$

where  $10^{(\bar{x})}$  is the GMT,  $\bar{x} = \sum \log_{10}(x)/N$ ,  $\log_{10}(x)$  is the log base 10 of the observed titer,  $N$  is the total observations in each vaccination group,  $\sqrt{v(\bar{x})}$  is the estimated standard deviation of  $\bar{x}$ ,  $\alpha = 0.05$ , and  $t_{n-1, \alpha/2}$  is the  $100(1 - \alpha/2)$  percentile of the central  $t$ -distribution with  $n-1$  degree of freedom.

##### *Confidence interval for the GMT ratio between 2 groups*

The calculations of the 95% CI for the GMT ratio between 2 groups are as following:

Logarithmic transformation of the individual titers will be calculated first. Assuming that individual  $\log_{10}$  (titer) is normally distributed, the 95% CI for the difference in  $\log_{10}$  (GMT) between group  $i$  and group  $j$  will be in the form:

$$\bar{X}_i - \bar{X}_j \pm t(1 - \alpha/2, n_i + n_j - 2) \cdot s \sqrt{1/n_i + 1/n_j},$$

where  $\bar{X}_i = \log_{10}$  (GMT) is the mean of  $\log_{10}$  (titer) of group  $i$ ,

$S^2 = [(n_i - 1)S_i^2 + (n_j - 1)S_j^2]/(n_i + n_j - 2)$  is the pooled sample variance,

$n_i$  and  $S_i^2$  are the sample size and sample variance of group  $i$ ,

$t(1 - \alpha/2, n_i + n_j - 2)$  is the  $100(1 - \alpha/2)$  percentile of the  $t$ -distribution with degrees of freedom (df) =  $n_i + n_j - 2$ .

### ***Confidence interval for the single proportion***

The 2-sided 95% CI for the single proportions will be constructed using the exact binomial method (Clopper-Pearson's method, quoted by Newcombe (1), i.e., using the inverse of the beta integral with SAS®):

Lower bound:  $1 - Beta(1 - \alpha/2, n - r + 1, r)$  and

Upper bound:  $Beta(1 - \alpha/2, r + 1, n - r)$

where  $\alpha = 0.05$ , and  $r$  is the observed number of events/responders in  $n$  observations.

### ***Confidence interval of the difference in proportions***

The 2-sided 95% CI of the difference in proportions will be computed using the Wilson Score method without continuity correction, quoted by Newcombe (2) as follows:

Let  $\hat{\theta} = \pi_A - \pi_B$ , then if  $L = \hat{\theta} - \delta$  and  $U = \hat{\theta} + \varepsilon$  are respectively the lower and the upper limits of the CI, where:

$$\delta = Z_{0.025} \sqrt{\left\{ \frac{l_1(1 - l_1)}{n_1} + \frac{u_2(1 - u_2)}{n_2} \right\}}$$
$$\varepsilon = Z_{0.025} \sqrt{\left\{ \frac{l_2(1 - l_2)}{n_2} + \frac{u_1(1 - u_1)}{n_1} \right\}},$$

$l_1$  and  $u_1$  are calculated from the CI of the single proportion in group A given by:

$$\frac{\left(2n_1p_A + Z_{0.025}^2 \pm Z_{0.025} \sqrt{\left(Z_{0.025}^2 + 4n_1p_A(1-p_A)\right)}\right)}{2(n_1 + Z_{0.025}^2)},$$

$l_2$  and  $u_2$  are calculated from the CI of the single proportion in group B given by:

$$\frac{\left(2n_2p_B + Z_{0.025}^2 \pm Z_{0.025} \sqrt{\left(Z_{0.025}^2 + 4n_2p_B(1-p_B)\right)}\right)}{2(n_2 + Z_{0.025}^2)},$$

where  $Z_{0.025}$  is the upper 97.5th percentile of the standard normal distribution.

